4.3 STAGE 2 PROCEDURES

4.3.1 Enrollment & Baseline

For Stage 2, subjects will be primarily consented and enrolled in person at the time of a previously scheduled appointment or procedure or via phone. If we are conducting procedures remotely, consent will be completed with subjects via phone by a study coordinator. Subjects will complete the Demographics and Health History questionnaire after informed consent procedures are

completed, and will also provide their contact information. The date that subjects consent is Study Day 1.

After enrollment, there is a run-in phase until 4+1 (28+7 days) weeks prior to implementation of the MTM intervention. Between Study Days 2 and 20 (11+9 days) of the run-in phase, subjects will undergo the 24-hour Diet Recall on two separate occasions, once either on a Tuesday or Wednesday and once on a Sunday or Monday in order to capture baseline weekday and weekend behaviors. A registered dietician from the University of Michigan Nutrition Obesity Research Center will call the subject directly in order to conduct the 24-hour Diet Recall via phone.

Baseline assessments will be conducted with all subjects at the end of the run-in phase within the 4+1 (28+7 days) weeks window. The study coordinator will complete assessments 1 – 6 in person with the subject. The subject will be provided the resources (website link and login information) during their study appointment to be able to complete the VioScreen FFQ at home within 1 day of their baseline visit. If a subject does not complete the baseline appointment in person, the subject will be withdrawn by study staff at that time. The assessments will be completed with each subject in the following order:

1. SF-8
2. PROMIS SE
3. EncephalApp Stroop
4. Liver Frailty Index
5. ANT
6. PROMIS IS
7. VioScreen FFQ

If the assessments will be completed with subjects remotely via phone, the EncephalApp Stroop and Liver Frailty Index will not be conducted. They will be conducted in the following order:

1. SF-8
2. PROMIS SE
3. ANT
4. PROMIS IS
5. VioScreen FFQ

4.3.2 Intervention

After baseline assessments are complete, the following steps to implement the MTM intervention with subjects will occur in clinic:

1. All subjects will receive Standard of Care (SOC), which is a standardized nutrition education handout containing instructions on following a high-protein+sodium restricted diet (depending on the presence of ascites).
2. All subjects will enroll in MTM designed and prepared by PurFoods, LLC (Des Moines, IA). PurFoods specializes in providing home-delivered, specialized dietitian-curated meals to patients with various medical conditions such as liver disease, chronic kidney disease, cancer and cardiovascular disease. Additional information about the company and their services can be found here: <https://www.momsmeals.com/>. Subjects will receive meals that adhere to their specified nutritional targets dependent upon their cirrhosis complication of hepatic encephalopathy and/or ascites. Subjects with HE will

receive high-protein (approx. 1g/kg/day) and high-calorie (approx. 30c/kg/day) meals. Subjects with HE and ascites will receive high-protein and high-calorie meals that are also low-sodium (<2000g/day). The study coordinator will place an order with PurFoods for each subject after their baseline assessments are complete. Subjects will select from an available menu of meal options each week that adhere to the specified nutritional targets as above. A staff member from PurFoods will contact the subject via phone or email to complete meal selection. Study food will be pre-packaged for storage with preparation (typically microwave heating) to be completed at home by the subject and will be delivered every 1 to 2 weeks under the direction of PurFoods.

3. In addition to home-delivered meals, the study coordinator will provide each subject with a daytime and nighttime protein supplement (approx. 15g protein) to be consumed daily at home during the same study days as MTM. The daytime protein supplement is a protein bar (ZonePerfect or Perfect Bar). The protein supplements will be provided to subjects in person after baseline completion or the study coordinator will ship them to the subject's home if in remote operations.

ZonePerfect Classic protein bars are shelf stable and contain 10 - 15g of protein per serving (1 bar). They do not contain any artificial sweeteners, flavors or colors. They come in the following flavors: strawberry yogurt, chocolate mint, oatmeal chocolate chunk, chocolate caramel cluster and others. Additional information can be found here: <https://zoneperfect.com/products>

The Perfect Bar is a refrigerated protein bar 14 – 17g of protein per serving (1 bar). Their primary source of protein are nut butters. They do not contain any artificial sweeteners, flavors or colors. Many of the flavors are lower in sodium (30-50g per serving), so these will function as a good option for subjects with ascites. They come in the following flavors: peanut butter, almond butter, blueberry cashew, mocha chip, among other. Additional information can be found here: <https://perfectsnacks.com/collections/bars>

There are two options for the nighttime supplement. The first option is a protein powder that can be dissolved in either water or milk. We are providing subjects with ProCel Chocolate Whey Protein powder which provides 15g of protein per serving. The second option is a liquid protein that can be mixed in a cup of water. We are providing subjects with LiquaCel Packets (assorted flavors) of liquid protein which provides 16g of protein per serving. Additional information regarding the protein supplements can be found here: <https://globalhp.com/shop/>

Once the MTM order is placed, subjects will receive meals at home within 3 – 5 days. The MTM will be pre-packaged for storage with preparation (typically microwave heating). Subjects are instructed to start eating the meals and protein supplements the day after they receive the meals from PurFoods. Subjects will consume meals and supplements daily for 6 weeks. Subjects will consume meals between approximately Weeks 4 – 11 of the study (SD 32±8 – 74±8). The actual dates of MTM for each subject will be dependent upon the date they complete their baseline appointment. During the final two weeks of MTM, subjects will undergo the 24-hour Diet Recall on two separate occasions, once either on a Tuesday or Wednesday and once on a Sunday or Monday in order to capture weekday and weekend behaviors. The study coordinator will call the subject to confirm the

date the subject started eating the meals and protein supplements, the diet recalls will occur within 28 to 42 days from this date. The date the 24-hour Diet Recall is completed is dependent upon the actual dates of the final two weeks of the intervention and this will vary per subject, but it will be completed between Weeks 8 – 11 for all subjects (SD 67±14). The dietitian will attempt to contact subjects via phone up to 4 times to complete the dietary interviews. The study coordinator will solicit questions related to dietary concerns during telephone calls once per week with each subject during the intervening weeks. The coordinator will also ask the subject if they know their current weight, and confirm that they have been eating the MTM.

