Once the MTM order is placed, subjects will receive meals at home within approximately 3 – 5 days. The MTM will be pre-packaged for storage with preparation (typically microwave heating). Subjects are instructed to start eating the meals and protein supplements the day after they receive the meals from PurFoods. Subjects will consume meals and supplements daily for 14 days, from Study Day 4(± 1) to Study Day 18(± 1). While the subjects are consuming MTM, subjects will undergo the 24-hour Diet Recall and VioScreen FFQ assessments between Study Days 9 – 17 (SD 13 ± 4). A registered dietitian from the University of Michigan Nutrition Obesity Research Center will call the subject directly in order to conduct the 24-hour Diet Recall via phone. The dietitian will attempt to contact subjects via phone up to 4 times to complete the dietary interview. For the VioScreen FFQ, the study coordinator will send the subject a link via email so they can complete the assessment at home via personal computer, tablet or smart phone. The study coordinator will also contact the subject via phone within the same time period to conduct a motivational call. During this call the subject will ask the subject if they know their current weight, confirm that they have been eating the MTM, and ask them if they've completed the VioScreen FFQ and if they have the coordinator will ask them for their thoughts on the assessment.

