4.3.3 Follow-Up & Outcomes

The first end point for Stage 2 is at the end of the MTM intervention. All subjects should complete the MTM intervention between Week 9 and 11; Study Days 66 and 82 (SD 74±8), barring any hospitalizations or other complications that may delay completion (see sections 4.4 and 4.5 below). The subjects will return for a second in-person visit within 2 weeks of completing intervention, between Weeks 9 and 13 (11±2 weeks); Study Days 66 and 96 (SD 81±15). At this visit, all baseline assessments will be repeated with the subject in the same order identified above (section 4.3.1). If we are conducting study procedures remotely, this visit will be conducted via phone. The EncephalApp Stroop and Liver Frailty Index will not be conducted in this circumstance. All subjects will be asked to complete the VioScreen FFQ at home within 2 weeks of completing the intervention (Weeks 9 and 13 (11±2 weeks); Study Days 66 and 96 (SD 81±15)).

Patients will then be observed for an additional 12 weeks from the date of second in-person visit. Subjects will be contacted biweekly via phone and/or email during this period to maintain contact. The main purpose of the phone calls during this time period is to maintain communication with the subject in order to prevent lost to follow-up. However, the study coordinator will also ask the subject to report their current weight. The observation period will be concluded with a phone assessment about healthcare utilization, an exit interview regarding their preferences and satisfaction with MTM (Appendix F), and the subject will also complete the ANT and SF-8. The final phone assessment represents the final end point of Stage 2 and will occur between Weeks 21 and 27 (24±3 weeks); Study Days 150 – 194 (SD 172±22).

The primary outcomes of Stage 2 are the subject retention rate at 24±3 weeks post-enrollment and the MTM intervention adherence rate at 9±2 weeks post-enrollment. Secondary outcomes measured at 24±3 weeks post-enrollment include proportion of subjects who complete all assessments and procedures, HRQOL (SF-8), cognitive function (ANT) and healthcare utilization rates and clinical outcomes. Other secondary outcomes include the proportion of subjects who complete all 24-hour Diet Recall interviews, the proportion of subjects who report improved nutritional intake and cognitive function assessed by the Encephalapp Stroop.

Table 2. Stage 2 Procedure Table

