5.2 ADVERSE AND SERIOUS ADVERSE EVENT DEFINITIONS & REPORTING

5.2.1 Adverse and Serious Adverse Event Definitions (AE & SAE)

In the BRAINFOOD study an AE is defined as any untoward or unfavorable physical, social or psychological occurrence in a participant that can be temporally associated with the subject's participation in the study, whether or not considered directly related to the subject's participation in the research. An AE is considered an SAE if the event results in death or permanent disability and is definitely related to the subject's participation in the study. However, due to the nature of the participants enrolled and low risk nature of the treatments, the AEs and SAEs recorded and reported to the IRB will be limited using the following guidance.

Events that are not attributable to their participation in the study will not be reported as AEs, even if the data are collected for study purposes (e.g. car accident, stroke, myocardial infarction etc.). The exception to this standard is death, which will always be reported as either an AE or SAE. Additionally, expected clinical issues that subjects experience related to their ongoing medical care or chronic health problems will not be considered AEs unless it involves any of the above mentioned AE examples. Any AEs that are attributable to the study will be reported and adhere to the AE Reporting Timeline (see Table 3 below). The 4 ± 1 week (Stage 1) and 24 ± 3 week (Stage 2) end points are our final contact with subjects in which we will collect AE and SAE information. Events which qualify as AEs will be classified using the following IRB standards:

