8.3 POTENTIAL RISKS AND BENEFITS

There is minimal medical risk to any participant in this study. Patients will be counselled on the risk of cirrhosis complications (ascites, HE) that may be related to their underlying disease as well as risks associated with meals (infections, nausea). Participants can withdrawal at any time. The potential benefits to participants include an improvement in QOL and reduction in ascites and the risk of HE.

The known or expected risks are:

- **Questionnaires:** Many of the questions relate to how the subjects are feeling, and this may lead to an emotional reaction. To minimize these risks, questions will not ask explicitly sensitive information and study coordinators will be available for support. Additionally, should the questionnaires or surveys become uncomfortable, subjects can choose to skip any question that they do not wish to answer or stop at any time.
- **Loss of confidentiality:** There is rare risk of loss of confidentiality or privacy. To reduce the risk of loss of confidentiality, trained members of the research team will ask subjects questions in a private patient room. Researchers will only provide (to the professionals trained in diet recall) the minimal amount of identifying information necessary in order to complete the diet recall. This information will be limited to the subject's name, date of birth, sex, and subject ID. The subjects name will only be used during the phone call and will not be reported with the diet recall data. Information such as the subject's full name and phone number will be recorded along with their baseline data however, this information will be stored in a locked cabinet. This data will be entered into a password-protected database where all data will be coded using a study number and only staff involved in this research will have access to the data.
- **Physical Assessments:** Assessments such as the chair stand test, 10-meter (33 feet) walk, and balance test may result in tiredness, dizziness upon standing, falling, pain, or injury. Though these risks are considered to be relatively minimal.
- **Medically Tailored Meals:** There is the possibility that these foods can cause unexpected allergic reactions or symptoms such as abdominal pain, diarrhea, nausea, or vomiting. Additionally, PurFoods provides meal delivery to the subjects home address. The researchers cannot be held responsible for meals that are not delivered for any reason.

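### No described contact systematically asks about the meal harms named in section 8.3, and no analysis summarises them, so tolerability is likely to be under-recorded

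*Combined protocol and SAP*

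**What the plan says.** Section 8.3 lists what the meals may cause: "unexpected allergic reactions or symptoms such as abdominal pain, diarrhea, nausea, or vomiting".

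The protocol outlines what is asked at each contact.

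- **Stage 1, on meals (section 4.2.2).** There is one motivational call, at which the coordinator is to "ask the subject if they know their current weight, confirm that they have been eating the MTM, and ask them if they've completed the VioScreen" questionnaire.
- **Stage 2, on meals (section 4.3.2).** "The study coordinator will solicit questions related to dietary concerns during telephone calls once per week with each subject during the intervening weeks". The next sentence reads: "The coordinator will also ask the subject if they know their current weight, and confirm that they have been eating the MTM".
- **Stage 2, observation period (section 4.3.3).** The calls serve mainly to keep contact. "However, the study coordinator will also ask the subject to report their current weight".
- **Final contacts (sections 4.2.3 and 4.3.3).** Stage 1 repeats most baseline assessments and adds the exit interview. Stage 2 covers healthcare utilization, the exit interview, the Animal Naming Test and the SF-8.

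Section 5.2.1 defines an AE broadly, and says of the Week 4 (Stage 1) and Week 24 (Stage 2) contacts that these "end points are our final contact with subjects in which we will collect AE and SAE information". It then narrows what is reported. Events not attributable to participation are left out, apart from death, and so in general are expected problems of the underlying illness. Attributable AEs are reported. Section 5.2.2 has the investigator grade relatedness, severity and expectedness, and section 5.2.3 sends AEs to the IRB. The endpoint list in section 1.2 and the analysis in section 6.2.1 contain no AE or tolerability summary.

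**The concern.** The protocol knows which symptoms the meals might cause, but does not say that anyone will ask every subject about them. A symptom reaches the data if the subject raises it or if an unspecified AE enquiry brings it out. It must then be judged attributable to the study. Nausea, diarrhea and abdominal pain may also come from cirrhosis or its treatment, and there is no control group to show the background rate, so that judgement is difficult.

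Two uses of the pilot are affected. Section 4.2.3 has the Stage 1 experience decide what changes in Stage 2. Adherence, meaning at least 75% of delivered meals and evening snack, is a Stage 2 primary endpoint. If adherence is low, the plan has no reliable way to tell intolerance from dislike. If few symptoms are recorded, a reader cannot tell good tolerability from incomplete enquiry.

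**Working it through.** **1. The plan's own figure.** There is none to reproduce. The documents give no symptom rate, and section 6.1 says the sample size does not come from a hypothesis test. The check is mainly a reading of each contact against section 8.3.

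**2. Contacts set against the named harms.**

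| Contact | Stated content | Asks about the named symptoms? |
|---|---|---|
| Stage 1 call, Study Day 13±4 | weight, eating the meals, food-frequency questionnaire | no |
| Stage 1 final visit, Day 28±7 | repeated assessments, exit interview | no |
| Stage 2 weekly calls on meals (6) | dietary concerns invited, weight, eating the meals | no |
| Stage 2 visit, Day 81±15 | repeated baseline assessments | no |
| Stage 2 observation calls (6) | contact, weight | no |
| Stage 2 final call, Day 172±22 | utilization, exit interview, Animal Naming Test, SF-8 | no |

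Tables 1 and 2 have no AE or symptom row. Appendix F asks about satisfaction, liking and suggestions. Its nearest item asks what was disliked, and only of subjects who would not eat the food again. The SF-8 asks about bodily pain over four weeks without locating it.

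**3. From symptom to result.** Even a symptom that is raised must pass the two exclusions in section 5.2.1. If it does, its stated destination is the IRB. No step leads to section 6.2.1.

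**4. Timing of the exit interview.** In Stage 1, meals end nominally on Day 18 and the interview is on Day 28: 28 − 18 = 10 days. In Stage 2, meals end on Day 74 and the interview is on Day 172: 172 − 74 = 98 days, or 14 weeks. The outer limits of the Stage 2 windows give 150 − 82 = 68 to 194 − 66 = 128 days.

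**5. Illustration of what incomplete asking does.** Let n = 20 (the Stage 2 minimum), p the true proportion with a given symptom, and c the share of affected subjects whose symptom is recorded. Both p and c are assumed. With independent subjects, P(none recorded) = (1 − p·c)^n.

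- p = 15%, c = 1/3: 0.95^20 = 0.36. With c = 1: 0.85^20 = 0.04.
- p = 20%, c = 1/3: (1 − 0.2/3)^20 = 0.25. With c = 1: 0.80^20 = 0.01.

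Over a wider range:

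| p | c = 1 | c = 0.5 | c = 0.25 |
|---|---|---|---|
| 10% | 0.122 | 0.358 | 0.603 |
| 20% | 0.012 | 0.122 | 0.358 |
| 30% | 0.001 | 0.039 | 0.210 |

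Pooling both stages (30 + 20 = 50) at p = 15% and c = 1/3 gives 0.95^50 = 0.08, if the rates were equal despite two weeks of meals against six.

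**6. Precision if everyone is asked.** Exact two-sided 95% intervals: 4/20 gives 6% to 44%, 0/20 has an upper limit of 17%, and 0/10 (one Stage 1 group) has an upper limit of 31%.

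**The case against.** The best defence is that the protocol does have an AE system. Sections 5.2.1 to 5.2.3 define, grade and report AEs. The weekly Stage 2 calls actively solicit dietary concerns and confirm that meals are being eaten, so intolerance could readily come up. Appendix F has open questions, asked in Stage 1 only about 10 days after the meals. The calls are summarised rather than scripted, and the intervention and outcome forms mentioned in section 7.1 are not shown. The narrow AE scope is a reasoned choice, which section 5.2.1 ties to the population and the low-risk intervention. Tolerability is not a stated objective.

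Much of this stands, and it rules out three stronger readings.

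- A reader might infer that AEs are collected only at the final contact, so that Stage 2 tolerability rests on recall over 14 weeks. The sentence in section 5.2.1 more naturally marks the end of a collection period. The 98 days apply to the exit interview, not to all AE capture.
- A reader might infer that a low recorded rate would simply mean nobody asked. The dietary-concerns prompt and the AE provisions make that too strong.
- A reader might infer that the definitive trial would adopt a faulty tolerability estimate. Nothing in the documents says so.

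The defence does not answer the central point. An open invitation is not the same question put to every subject, no elicitation method is described, and no summary is planned. The reasons given for limiting IRB reporting do not bear on collecting tolerability data separately.

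**Conclusion.** The point holds in a limited form. AE information is said to be collected, but no described contact systematically elicits the harms named in section 8.3. The attribution and chronic-disease exclusions may remove them, and no endpoint or analysis summarises them. Under-recording is likely. Its size cannot be established, because the documents give neither symptom rates nor capture rates. Whether the exception to the chronic-disease exclusion would bring these symptoms back in also cannot be settled, since the examples it refers to are not identifiable in the available text.

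The contrast of 36% with 4% is an illustration on an assumed 15% symptom rate and one-third capture, for one symptom in 20 subjects. It should not be read as a forecast for this trial, and it shrinks if capture is better or the stages are pooled. This is a worthwhile, inexpensive improvement. It does not undermine the retention or adherence endpoints themselves.

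**What to change.** Add one fixed checklist: abdominal pain, diarrhea, nausea, vomiting and allergic reaction, each yes or no, with the date and whether the subject stopped eating the meals. Give it:

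- before meals start (Stage 1 Day 1 and the Stage 2 baseline visit), asking about the past week;
- at the existing Stage 1 call and the weekly Stage 2 calls, asking about the time since the last contact;
- at the Stage 1 Week 4 and Stage 2 Week 11 visits, asking in the same way.

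Record it for every subject as tolerability data, whether or not a symptom is thought attributable. Leave the IRB AE reporting rules and all clinical management unchanged.

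Add to section 6.2.1 a descriptive table of n/N and percent with each symptom before and on meals, by stage, with exact 95% intervals. State the look-back period beside each figure, because a cumulative on-meal figure covers more time than a single baseline question.

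The cost is about a minute per contact, one REDCap form and one table, with no extra contacts. Reported symptom rates will be higher and will include background symptoms of cirrhosis. The pre-meal checklist helps to interpret these, but without a control group it cannot fully separate them from effects of the meals.
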